4.2.2 Inclusion Criteria

For inclusion in the investigation, the subjects must fulfil all of the below criteria prior to enrolment:

1. Signed Informed Consent Form
2. Both gender ≥ 18 years old
3. From Medium (defined as Wet specified in section 4.5.6) to High exuding (defined as Leaking specified in section 4.5.6) wound

4.2.3 Exclusion Criteria

Subjects who meet any of the below criteria will be excluded from the investigation

1. Known allergy/hypersensitivity to any of the treatment dressings
2. Pregnant/lactating females
3. Subjects with a target wound that is $\leq 1 \text{ cm}^2$
4. Subjects with a target wound that is a full thickness burn
5. Subjects with known immunodeficiency
6. Subject taking systemic antibiotics for wound infection
7. Subject where the target wound is located on an infected limb interfered by minimal blood flow (in the opinion of the investigator).
8. Subject with a target wound with unexplored enteric fistula
9. Subjects who, in the opinion of the investigator, will have problems following the protocol
10. Subjects needing treatment with oxidizing agents such as hypochlorite solutions or hydrogen peroxide
11. Previously enrolled in the present investigation
12. Inclusion in other ongoing investigations at present that would preclude the subject from participating in this investigation as judged by the investigator
13. Involvement in the planning and conduct of the clinical investigation (applies to all Mölnlycke staff, investigational site staff and third party vendor)

4.2.4 Withdrawal of Subjects from Treatment or Assessment

Subjects are free to discontinue participation in the investigation at any time, and without prejudice to further treatment. Subjects who discontinue the investigation should always be asked about the reason(s) for their discontinuation and about the presence of any Adverse Event/Adverse Device Effect or Device Deficiency and, if possible, be assessed by an investigator. Adverse Event/Adverse Device Effect should be followed up.

Subjects may be withdrawn from investigation treatment and assessments at any time, at the discretion of the investigator.

Incorrectly enrolled subjects will be withdrawn from further investigation treatment and assessments. A subject may, however, continue the investigation under special circumstances (i.e. if continuation of investigation treatment or follow-up actions are necessary for the subject's safety and well-being, or if only a follow-up period remains, and the continuation of the investigation is not expected to be associated with any risk or discomfort for the subject).

Clinical Investigation Plan

Document ID: PD-523857 Rev: 01

Title: CIP with integrated central Amendments 1 and 2 ExufiberAg+01

Page 25(50)

Investigation Code	ExufiberAg+01Final Version	Approval date	2017-05-10
		Amendment 1 Approval date	2017-05-26
		Amendment 2 Approval date	2018-08-07
		Amendment 3 Approval date	2018-08-21
		Amendment 4 Approval date	2019-02-19

Title: CIP with integrated central Amendments 1 and 2 ExufiberAg+01

Page 26(50)

Investigation Code	ExufiberAg+01Final Version	Approval date	2017-05-10
		Amendment 1 Approval date	2017-05-26
		Amendment 2 Approval date	2018-08-07
		Amendment 3 Approval date	2018-08-21
		Amendment 4 Approval date	2019-02-19

4.3 Investigational Device

4.3.1 Summary description of the Investigational Device(s)

Exufiber Ag+

Exufiber Ag+ wound dressing is a sterile, soft and nonwoven pad. Exufiber Ag+ consists of highly absorbent and gel forming polyvinyl alcohol (PVA) nonwoven fibres. The nonwoven pad is coated with silver sulphate on both sides. The silver is released within the dressing in contact with fluid, and acts as a preservative in the dressing to inhibit or reduce microbial growth in the dressing. The investigational device fall under FDA-premarket notification K160379. The dressing is sterilized in EtO (ethylene oxide).

For this clinical investigation, Exufiber Ag+ will be available in the following size:

Dressing sizes		Total silver content
cm	Inches	mg
5x5	2x2	5
15x15	6x6	45

Manufacture registered trademark of Mölnlycke Health Care AB.

Exufiber

Exufiber is a sterile nonwoven dressing made from highly absorbent and gel forming polyvinyl alcohol fibres. Exufiber is available as pad. Exufiber wound dressing absorbs and retains wound exudate. It is transformed into a soft gel that facilitates moist wound healing and ease of removal during dressing change. The investigational device is exempt and fall under FDA regulation number 878.4018 The dressing is sterilized in EtO.

For this clinical investigation, Exufiber will be available in the following size:

Dressing sizes	
cm	Inches
5x5	2x2
15x15	6x6

Manufacture registered trademark of Mölnlycke Health Care AB.

Aquacel Ag Extra

Dressing with Silver and Strengthening Fibre is a one piece wound dressing comprised of two layers of soft, sterile non-woven material. The non-woven pads are comprised of Hydrofiber dressing and ionic silver stitch bonded together with regenerated cellulose fibres and designed to provide additional absorbency and tensile strength properties. The investigational device fall

Title: CIP with integrated central Amendments 1 and 2 ExufiberAg+01

Page 27(50)

Investigation Code	ExufiberAg+01Final Version	Approval date	2017-05-10
		Amendment 1 Approval date	2017-05-26
		Amendment 2 Approval date	2018-08-07
		Amendment 3 Approval date	2018-08-21
		Amendment 4 Approval date	2019-02-19

under FDA-premarket notification K121275. The dressing is sterilized by radiation. For this clinical investigation, Aquacel Ag Extra will be available in the following size:

Dressing sizes		Total silver content
cm	Inches	mg
5x5	2x2	4.5
15x15	4x4	40.5

Manufacture registered trademark of ConvaTec Inc.

For more information regarding the dressings, instructions for use and precautions see Appendix D, Instruction for use.

4.3.2 Additional products

All additional products must be record in the "Dressing Log". The secondary dressing will be chosen according to local routine.

4.3.3 Labelling

Mölnlycke will provide the investigational devices to the investigation site for free, the study dressings should only be used within the clinical investigation.

The Exufiber Ag+ is a 510(k) cleared device the additional labels are just there to assist the study site in identifying investigational device.

Exufiber and Aquacel Ag Extra will not be labelled with an extra label. Labelling of the investigational medical device will be performed in accordance with Good Manufacturing Practice (GMP). The labels will be produced in the local language and in accordance with local regulations for the US.

The Exufiber Ag+ will be labelled with the following text:

Exufiber Ag+

Study code: Exufiber Ag+ 01

Investigational device – Not for Resale

4.3.4 Accountability

The investigational device dressings will not be distributed to the investigation site until all agreements between the investigator and Mölnlycke are finalized and IRB approval has been obtained. All investigational device dressings must be kept in a secure place under appropriate storage conditions.

Use of Exufiber Ag +, Exufiber, Aquacel Ag Extra and the secondary dressing will be recorded in the "Dressing Log" and will be reviewed at each monitoring visit. The investigational device may only be used in this clinical investigation and according to the CIP.

Title: CIP with integrated central Amendments 1 and 2 ExufiberAg+01

Page 28(50)

Investigation Code	ExufiberAg+01Final Version	Approval date	2017-05-10
		Amendment 1 Approval date	2017-05-26
		Amendment 2 Approval date	2018-08-07
		Amendment 3 Approval date	2018-08-21
		Amendment 4 Approval date	2019-02-19

The principal investigator or an authorized designee shall keep records documenting the receipt, use, return and disposal of the investigational devices.

Unused products are accounted for and returned to Mölnlycke for destruction, or destroyed locally upon agreement with and approval from Mölnlycke.

Applicable documents are the "Certificate of Delivery of Investigational Device/Material" and the "Certificate of Return and Destruction of Investigation Product".

4.3.5 Storage conditions

Investigational device dressings are to be handled and stored safely (locked place), properly and in agreement with the given storage instructions.

A description of the appropriate storage and shipment conditions are specified on the investigational device label and in the instructions for use documentation (IFU), Appendix D.

4.3.6 Method of Assigning Subjects to Treatment Groups

Subjects will be assigned according to section 4.1. The first eligible 50 subjects will be assigned by the investigator to Exufiber Ag+, Subjects 51 to 65 will be assigned to Exufiber, Subjects 66 to 85 will be assigned to Aquacel Ag Extra and recorded in the eCRF. Subjects 86 to 105 will be assigned to Exufiber Ag+ on eligible pressure ulcer subjects. Mölnlycke or delegate will notify the study investigator when each treatment group has been fully enrolled. Each treatment group may be adjusted due to enrolment by approximately 20%.

The secondary dressing will be chosen according to local routine.

If a subject discontinues from the investigation, the Subject ID will not be reused and the subject will not be allowed to re-enter the investigation.

4.4 Concomitant Treatments

Medication, which is considered necessary for the subject's safety and well-being, may be given at the discretion of the investigator. Except the study dressings, usage of other antimicrobial dressings or antimicrobial topical agents on the target wound during the study is not allowed.

All relevant concomitant medication that may have an impact of the wound condition, safety for the subject or may affect the evaluation of dressings performance as justified by the investigator should be recorded in the appropriate section of the electronic Case Report Form (eCRF).

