Wounds that produce an excessive amount of exudate is in an, inflammatory state. By reducing exudate the conditions for bacterial growth become less optimal. Gelling fibre dressings are developed to absorb and retain large amount of exudate to support an optimal wound healing process. Gelling fibre dressings with additional silver ions have *in vitro* models shown to decrease the number of microorganisms.

Delayed healing often defined as clinical signs of infection (exudate, pain, discolouration, odour)⁶. Infected wounds are likely to be more painful and associated with high exudate levels which can increase the number of dressing changes required. The negative effect on excess exudate on wound healing can result in delayed healing, maceration of peri-wound skin and embarrassing

Title: CIP with integrated central Amendments 1 and 2 ExufiberAg+01

Page 16(50)

Investigation Code	ExufiberAg+01Final Version	Approval date	2017-05-10
		Amendment 1 Approval date	2017-05-26
		Amendment 2 Approval date	2018-08-07
		Amendment 3 Approval date	2018-08-21
		Amendment 4 Approval date	2019-02-19

leakage for the patient. It is important that modern wound dressing can maintain moisture balance by absorbing excess exudate and preventing the wound drying out, in addition to being able to afford bacterial barrier properties in the wound are risk of infection, when required⁷. Majority of the silver dressing studies have included endpoints related to healing, however more appropriate endpoints for silver dressing may related to measure microbial burden or assessment of clinic indicators of infection⁸.

The current golden standard of antimicrobial gelling fibre dressings is today Aquacel Ag and its further developed range of products such as Aquacel Ag Extra and Aquacel Ag+ Extra (not on the US only EU market). A new antimicrobial gelling fibre dressing (Exufiber Ag+) has been developed and is 510(k) cleared for sales in the United States.

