4.5 Performance and Safety

4.5.1 Subject Characteristics

Date of birth	DD/MMM/YYYY
Gender	Male/Female

Title: CIP with integrated central Amendments 1 and 2 ExufiberAg+01
Page 29(50)

Investigation Code	ExufiberAg+01Final Version	Approval date	2017-05-10
		Amendment 1 Approval date	2017-05-26
		Amendment 2 Approval date	2018-08-07
		Amendment 3 Approval date	2018-08-21
		Amendment 4 Approval date	2019-02-19

Vital signs	Height (cm/feet and inches) Weight (kg/pounds) BMI
Relevant Medical History Relevant such as diabetes, arterial disease lower leg, anemia, cardio-vascular disease, thrombosis, that may affect the evaluation of dressings performance	Medical condition Date of initial diagnosis Past/current Ongoing medication
Relevant Surgical History Relevant such as varicose vein, amputation defined as surgery that may affect the evaluation of dressings performance.	Surgical procedure Date of surgical procedure Past/current Ongoing medication
Type of wound and location of the wound	Venous leg ulcer Arterial leg ulcer Mixed etiology Pressure ulcers (partial) Diabetic foot ulcer Traumatic wounds Partial thickness burns (second degree) Donor site Malignant wounds
Duration of wound	< 1 week ≥ 1 week to <6 weeks ≥ 6 weeks to <12 month ≥12 month

Title: CIP with integrated central Amendments 1 and 2 ExufiberAg+01
Page 30(50)

Investigation Code	ExufiberAg+01Final Version	Approval date	2017-05-10
		Amendment 1 Approval date	2017-05-26
		Amendment 2 Approval date	2018-08-07
		Amendment 3 Approval date	2018-08-21
		Amendment 4 Approval date	2019-02-19

Current wound treatment	Primary dressing (Y/N) Name of the current primary dressing Frequency of dressing change/per week Secondary dressing (Y/N) Name of the current secondary dressing
-------------------------	---

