4.5.4 Identification and quantification of microorganisms presents in the wound

[figure not shown]
This section is only applicable for site no 01 (only subjects enrolled before September 2018) since they are the only site collecting tissue and exudate.

Evaluation of antimicrobial activity of Exufiber Ag+ and Exufiber on wound bioburden by collection of tissue and exudate (specified in Appendix F). Following analysis will be performed on approximately 30 subjects, equally distributed between Exufiber Ag+ and Exufiber.

- ✓ overall quantification of microbial counts by traditional culturing under aerobic conditions
- ✓ identification of bacteria/fungi by Next Generation Sequencing (16S rRNA for bacteria, ITS1 or ITS2 for fungi)
- ✓ evaluate inflammatory biomarkers and virulence factors via collecting wound exudate

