4.7 Statistical Methods and Determination of Sample Size

4.7.1 Statistical Evaluation

General Methodology

The main focus and analysis will be the analysis of the subjects treated with Exufiber Ag+.

The main analyses will be change in primary and secondary efficacy endpoints from baseline to 4 weeks on the ITT population in this group treated with Exufiber Ag+. If missing values at 4 weeks

Title: CIP with integrated central Amendments 1 and 2 ExufiberAg+01

Page 41(50)

Investigation Code	ExufiberAg+01Final Version	Approval date	2017-05-10
		Amendment 1 Approval date	2017-05-26
		Amendment 2 Approval date	2018-08-07
		Amendment 3 Approval date	2018-08-21
		Amendment 4 Approval date	2019-02-19

last observation carry forward (LOCF) will be applied from 1 week.

A sensitivity analysis will be performed for primary analysis with complete cases.

Complementary analyses will be performed on the PP population and for change from baseline to 3 days, 1 week, 2 weeks and 3 weeks.

Since primary efficacy variable and most of the secondary efficacy variables are ordered categorical or dichotomous variables the Sign test will be used for analysis of change within groups for these types of variables and described with number and percentages of improved, not changed and worsened. For primary efficacy variable and important secondary efficacy variables a complete cross tabulation baseline and 4 weeks will be given.

All significance test will be two-sided and conducted at the 5 % significance level.

Continuous variables will be described with mean, SD, median, minimum and maximum and categorical variables will be given with number and percentages. All measured variables will be described by visit.

The statistical analysis of the groups treated with Exufiber or Aquacel Ag Extra will be analysed separately with the same statistical methods as specified above. The database for Exufiber Ag+ will be declared clean and will be analysed before the other two treatment groups are finalised.

Patient Disposition and Data Sets Analysed

The number of subjects included in each of the ITT, PP and safety populations will be summarized. The number and percentage of subjects enrolled and treated will be presented.

Subjects who completed the study and subjects who withdrew from study prematurely will also be presented with a breakdown of the reasons for withdrawal for the ITT, PP and safety populations.

Protocol Violations/Deviations

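### The bioburden part aims at antimicrobial activity but analyses each dressing only within group, so silver cannot be separated from everything else that changes counts; unknown baseline carry-over is a lesser problem

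*Combined protocol and SAP*

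**What the plan says.** **Purpose and sample.** Section 4.5.4 describes the bioburden work as "Evaluation of antimicrobial activity of Exufiber Ag+ and Exufiber on wound bioburden by collection of tissue and exudate". On numbers it says: "Following analysis will be performed on approximately 30 subjects, equally distributed between Exufiber Ag+ and Exufiber". Only site 01 takes samples, and only from subjects enrolled before September 2018. Section 4.3.1 describes both dressings as gelling polyvinyl alcohol fibre, one coated with silver sulphate and the other without silver.

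**Endpoint and analysis.** Section 4.5.2 defines the outcome as change from baseline in log CFU/cm² and in microbial diversity at Visits 1b, 2 and 3 (days 4, 7 and 14). Section 4.7.1 puts the main focus on Exufiber Ag+ and continues: "The statistical analysis of the groups treated with Exufiber or Aquacel Ag Extra will be analysed separately with the same statistical methods". Section 4.7.2 likewise keeps secondary variables within treatment groups. Section 4.7.1 also has the Exufiber Ag+ data cleaned and analysed before the other two groups are complete. No Exufiber Ag+ versus Exufiber comparison is planned.

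**Antimicrobials before and during the study.** Section 4.4 says that "usage of other antimicrobial dressings or antimicrobial topical agents on the target wound during the study is not allowed". The nearest exclusions in section 4.2.3 are number 6, "Subject taking systemic antibiotics for wound infection", and number 10, "Subjects needing treatment with oxidizing agents such as hypochlorite solutions or hydrogen peroxide". Neither sets a look-back period or mentions earlier antimicrobial dressings. Section 4.5.1 collects "Name of the current primary dressing" at baseline, but no planned analysis uses it beyond a baseline summary.

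**The concern.** An aim of judging antimicrobial activity needs some way to tell silver from everything else that can move a wound's bacterial count over two weeks. Section 4.5.2 records cleansing and debridement by visit, the schedule in 4.2.1 takes tissue at four visits, and wounds have their own course. All of these sit inside the change from baseline on Exufiber Ag+. The silver-free Exufiber subjects, sampled at the same site on the same schedule, are the only available reference for them, and the plan does not use them as one.

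The smaller issue is the baseline itself. A subject may come to Visit 1 directly from an antimicrobial dressing and be sampled while its effect persists. Starting from a lowered count, Exufiber Ag+ would show too small a fall, and Exufiber could show a rebound.

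What is at stake is the reading of the results. Two separate within-group summaries invite the statement that counts fell on the silver dressing and therefore silver worked.

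**Working it through.** **1. The plan's own figure.** The only sample-size calculation is in 4.7.3, for exudate: 56.5% improved, 32.9% unchanged, 10.6% worsened. The share changing is 0.565 + 0.106 = 0.671, and the share of those improving is 0.565/0.671 = 0.842. The exact two-sided Sign test, averaged over the number of changed subjects, gives power 94.6% at n = 38 and 95.2% at n = 39. For dropout, 38/0.8 = 47.5, so 48 against the 50 planned. The figure is reproduced closely enough. It says nothing about bioburden, for which the documents give neither a sample-size basis nor an SD.

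**2. What each analysis estimates.** Let S be the silver effect, C the change from all non-silver causes, and K the shift from carry-over at baseline.
- Change on Exufiber Ag+ = S + C + K(Ag+).
- Change on Exufiber = C + K(Exufiber).
- Difference = S + [K(Ag+) − K(Exufiber)], if C is the same in both groups.

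Only the difference removes C. The planned analyses report the first two lines and never the third.

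**3. Size of the attribution problem (illustration).** Section 4.7.1 gives continuous variables descriptive statistics and names no test for log CFU, so a two-sided 5% one-sample t-test is assumed, with n = 30/2 = 15. Set S = 0 and K = 0, and let both groups share a non-silver fall of e SDs of change. The noncentrality is e × √15 with 14 df. Let p be the chance that Exufiber Ag+ is significant. The chance that Exufiber Ag+ is significant and Exufiber is not is p(1 − p).

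| e (SD) | p | p(1 − p) |
|---|---|---|
| 0.25 | 0.145 | 0.124 |
| 0.50 | 0.438 | 0.246 |
| 0.75 | 0.771 | 0.177 |
| 1.00 | 0.949 | 0.048 |

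So with no silver effect at all, the within-group result is often significant, and comparing the two verdicts by eye is no safe substitute for a contrast.

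**4. Precision of the contrast.** Half-width of the 95% CI, before baseline adjustment = t(0.975, 28) × SD × √(2/15).
- Assumed SD 1.0 log: 2.048 × 1.0 × 0.365 = 0.75 log.
- Assumed SD 1.5 log: 2.048 × 1.5 × 0.365 = 1.12 log.

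With the 20% group-size tolerance in 4.3.6, the half-width is 0.85 SD at 12 per group and 0.68 SD at 18. At 15 per group the difference detectable with 80% power is 1.06 SD. Power for a 1-log difference is 75% at SD 1.0 and 42% at SD 1.5.

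**5. Carry-over.** Suppose a share f of subjects arrives with the baseline count lowered by s log, and later counts no longer depend on the earlier dressing. Each group's mean change then shifts upward by f × s. Neither input is in the documents. Assuming f = 0.2 to 0.4 and s = 0.5 to 1.5, the shift runs from 0.2 × 0.5 = 0.1 to 0.4 × 1.5 = 0.6 log. In the difference only [f(Ag+) − f(Exufiber)] × s remains. This is zero for equal shares; with 0.4 in one group and 0.2 in the other, it is 0.2 × 1.5 = 0.3 log at the upper value of s. The contrast therefore removes most of the carry-over problem unless the shares differ between groups.

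**The case against.** The strongest reply is that the objective listed in section 2 asks only how bioburden changes between baseline and Visit 3, and a within-group description answers that. The reference to antimicrobial activity appears in the procedural section 4.5.4, where it covers the silver-free dressing too, so it may be loose wording. This stands: the listed objective can be met as planned. The gap is between the purpose in 4.5.4 and the analysis in 4.7.

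A second reply is that the contrast is itself weak. Section 4.3.6 assigns the first 50 subjects to Exufiber Ag+ and numbers 51 to 65 to Exufiber, so dressing is confounded with enrolment period. Sampling covers only subjects enrolled before September 2018, and the Exufiber Ag+ data may be analysed first, so a contrast added late could be post hoc. This also stands and limits what the contrast can be called.

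Third, part of the problem is already covered by recording: the prior primary dressing, cleansing, debridement and concomitant medication are all collected. That makes the repair possible but does not carry it out. Appendices D and F are not in the supplied text, so how tissue is taken, and how much the sampling itself alters counts, cannot be judged.

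A reader might infer that many subjects come straight from silver, because the introduction states: "The current golden standard of antimicrobial gelling fibre dressings is today Aquacel Ag". That sentence ranks products within one class and does not describe usual care for exuding wounds. Section 4.5.1 also admits donor sites, burns, traumatic wounds and wounds under one week old, many of which may have had no earlier silver dressing. The documents support no figure for prior use.

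**Conclusion.** The point holds as a mismatch between purpose and analysis. The stated purpose of the bioburden sampling is antimicrobial activity, and the plan reports only separate within-group changes, which cannot attribute a fall in log CFU to silver. The illustrative error rates rest on an assumed t-test, 15 subjects and a shared non-silver fall; the size of any such fall is unknown.

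A reader might go further and infer that the lack of a pre-study restriction by itself undermines the bioburden objective. The documents do not support this. Carry-over mainly hides an effect of Exufiber Ag+ rather than creating one, it largely cancels in a between-dressing difference, and its frequency is unknown. Under the assumptions shown, its 0.1 to 0.6 log is smaller than the 0.75 to 1.12 log half-width of the contrast.

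Nor would the contrast prove antimicrobial activity: about 15 against 15, assigned in sequence without randomisation, is descriptive evidence. The objective is secondary, and the primary exudate analysis and its sample size are untouched. Making the change is worthwhile because it is cheap.

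**What to change.** In section 4.7.2, for the sampled site 01 subjects:

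1. Report the Exufiber Ag+ minus Exufiber difference in log CFU change at days 4, 7 and 14, adjusted for baseline log CFU, with a 95% CI, once both groups are available. Label it descriptive, because assignment is sequential and non-randomised and the groups are small. If it is added after the Exufiber Ag+ data have been analysed, label it post hoc.
2. As a sensitivity analysis, repeat this without subjects whose recorded pre-study primary dressing was antimicrobial. State that this field does not capture earlier topical agents, so the classification is incomplete.
3. Make no claim of antimicrobial activity from the within-group change on Exufiber Ag+ alone. Limit such statements to describing change, and read them alongside the contrast and its confounding with enrolment period. Align the wording of 4.5.4 accordingly.

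The cost is plan wording and one small analysis on data already collected. The downside is low precision, and lower still in the sensitivity analysis, which uses fewer than 30 subjects if any are set aside.
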